5.3 Efficacy Evaluation

For the primary endpoint the ITT population will be used. For the secondary endpoints the ITT population or FAS will be used as described above.

Mean, standard deviation, median, minimum and maximum for the continuous variables and absolute and relative frequencies for the categorical variables are presented both overall and separately for the randomized groups for each time point. Numbers of missing observations are presented for the randomized groups separately for each time point.

5.3.1 Analysis of Primary Endpoint

A linear model (ANCOVA) will be used with the following variables:

- Dependent variable:
 - AUC value based on DESS scores t2-t9 (see Section 5.1.1)
- Independent variables:
 - Random group as two factors (i.e. 1st factor: treatment discontinuation vs continuation; 2nd factor; high vs. medium expectation) and their interaction
 - The following stratification variables of the randomization process:
 - *intake duration with 24 months as a marker for long-term intake (<24 months of AM vs. >24 months)*
 - *risk of developing discontinuation symptoms associated with the antidepressant medication (moderate vs. higher or unknown risk)*
 - The corresponding pseudo baseline value (t1) will additionally be included as covariate.

Primary interest lies in the interaction between the two factors describing the random group. The post-hoc comparisons between the subgroups will be addressed exploratively. If the corresponding p-value (for the interaction) is >0.15 the model will be calculated without the interaction and the independent main effects of the 2 factors will be assessed.

Normal distribution of the residuals will be checked graphically via a histogram of residuals. If the assumption of normally distributed residuals is clearly violated, a sensitivity analysis using the log-transformation for the dependent variable will be performed to judge the robustness of the results.

Adjusted mean values and adjusted effect estimators (mean differences) with corresponding 95% Wald confidence intervals and p-values will be given.

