1.2 Study Objective

This study aims to disentangle pharmacological from expectation effects and their interaction during discontinuation of antidepressants and explore their underlying processes. More specifically the following questions and hypotheses were stated:

- How do treatment and treatment expectation contribute to discontinuation symptom load? Treatment (discontinuation of AM vs. continuation) and treatment expectation (high vs. medium) interact in modulating discontinuation symptom load among remitted major depressive disorder (MDD) patients over the course of the experimental phase.
- In what way can discontinuation symptom load be affected by treatment expectation, i.e. the placebo-effect, alone? Remitted MDD patients who remain on their antidepressant medication will show a higher discontinuation symptom load with moderate than with high expectation.
- In what way can the discontinuation symptom load be affected by pharmacological factors alone? Remitted MDD patients with moderate treatment expectation will show a higher discontinuation symptom load if antidepressant medication is discontinued versus if antidepressant medication is continued.
- In what way does the discontinuation symptom load differ between high and moderate treatment expectation? Remitted MDD patients who discontinue their antidepressant

medication will show a higher discontinuation symptom load with high than with moderate treatment expectation.

- The relationship between treatment expectation and discontinuation symptom load will vary according to stress ratings, prior side effects of antidepressant medication, prior discontinuation experience, neuroticism, anxiety, somatosensory amplification, and illness framework.

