2.1 Trial Design

PHEA is a prospective, randomised, parallel-group, partly blinded, open-hidden discontinuation trial with a 2x2-factorial design. The allocation ratio is 1:1:1:1 for the four groups:

- Treatment discontinuation and high expectation - open discontinuation (OD):
Patients in this group receive gradually decreasing doses of prescribed AM in encapsulated tablets and will receive full information about their treatment (i.e., high expectation).
- Treatment continuation and high expectation - open continuation (OC):
Patients in this group remain on prescribed AM in identical encapsulated tablets and will receive full information about their treatment (i.e., high expectation).
- Treatment discontinuation and medium expectation - hidden discontinuation (HD):
Patients in this group will receive gradually decreasing doses of prescribed AM in encapsulated tablets and will be informed about a 50% chance of discontinuing versus remaining on AM (i.e., moderate expectation).
- Treatment continuation and medium expectation - hidden continuation (HC):
Patients in this group will remain on prescribed AM in identical encapsulated tablets and will be informed about a 50% chance of discontinuing versus remaining on AM (i.e., moderate expectation).

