5.3.2 Analysis of Secondary Endpoints

Continuous outcomes

Linear models (ANCOVA) will be used with the following variables:

- Dependent variables:
 - AUC value based on DESS scores week 14 till week 52, i.e., assessed at FU1-FU3
 - Change from baseline (t1) of patient-reported stress scores based on PSS-10 scores at t9 (12 weeks after t1)

- Change from baseline (t1) of patient-reported state-anxiety scores based on STADI scores at t9 (12 weeks after t1)
- Independent variables:
 - Random group as two factors (i.e. 1st factor: treatment discontinuation vs continuation; 2nd factor; high vs. medium expectation) and their interaction
 - The stratification variables of the randomization process:
 - *intake duration with 24 months as a marker for long-term intake (<24 months of AM vs. >24 months)*
 - *risk of developing discontinuation symptoms associated with the antidepressant medication (moderate vs. higher or unknown risk)*
 - Concerning secondary endpoint a), the corresponding pseudo baseline value (t1) will additionally be included as covariate.

Primary interest lies in the interaction between the two factors describing the random group. The post-hoc comparisons between the subgroups will be addressed exploratively. If the corresponding p-value (for the interaction) is >0.15 the model will be calculated without the interaction and the independent main effects of the 2 factors will be assessed.

Normal distribution of the residuals will be checked graphically via a histogram of residuals. If the assumption of normally distributed residuals is clearly violated, a sensitivity analysis using the log-transformation for the dependent variable will be performed to judge the robustness of the results. Adjusted mean values and adjusted effect estimators (mean differences) with corresponding 95%-Wald confidence intervals and p-values will be given.

The ICC (intra-class correlation) will also be reported, where appropriate.

Linear mixed model (random intercept model) will be used with the following variables:

- Dependent variable:
 - Bias score (emotional versus neutral faces, measured in ms)
- Independent variables (fixed factors):
 - Expectation concerning recurrence of discontinuation symptoms derived from the factors of the random group: high expectation (open discontinuation group) versus moderate expectation (both hidden groups, continuation and discontinuation) versus low expectation (open continuation group)

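### The primary interaction contrast is the sum of two expectation steps, so significance alone cannot separate additive drug and expectation effects from a drug-by-expectation interaction

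*SAP*

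**What the plan says.** SAP 2.1 sets up four arms and labels both open arms as high expectation; the continuation arm is introduced as "Treatment continuation and high expectation - open continuation (OC"). The two hidden arms, told of a 50% chance of discontinuing, are labelled medium or moderate.

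SAP 5.3.1 carries these labels into the primary ANCOVA of the DESS area under the curve ("Random group as two factors (i.e. 1st factor: treatment discontinuation vs continuation; 2nd factor; high vs. medium expectation) and their interaction") and adds: "Primary interest lies in the interaction between the two factors describing the random group". If the interaction p-value exceeds 0.15, the interaction is dropped and the two main effects are assessed. Subgroup comparisons are post hoc and exploratory.

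The first hypothesis in SAP 1.2 is "Treatment (discontinuation of AM vs. continuation) and treatment expectation (high vs. medium) interact in modulating discontinuation symptom load". Two further hypotheses there give directions. On continued drug, "Remitted MDD patients who remain on their antidepressant medication will show a higher discontinuation symptom load with moderate than with high expectation", that is, HC above OC. Off drug the direction is reversed: more symptoms with high than with moderate expectation, that is, OD above HD.

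For the Posner endpoint, SAP 5.3.2 defines "Expectation concerning recurrence of discontinuation symptoms derived from the factors of the random group", with the levels "high expectation (open discontinuation group) versus moderate expectation (both hidden groups, continuation and discontinuation) versus low expectation (open continuation group").

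**The concern.** Open continuation is high on one expectation variable and low on the other, and the SAP never relates the two. The directional hypotheses for the DESS make sense only with the second ordering: being told openly that the drug continues should lower expected discontinuation symptoms, and being told openly that it stops should raise them. So the second factor in the primary model is not a scale of symptom expectation. It is open versus hidden information, and its effect on expectation changes sign between the drug conditions.

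This affects how the only confirmatory test is read. The study aims to separate drug effects, expectation effects and their interaction. A term that is non-zero whenever expectation matters cannot by itself show that drug and expectation effects depend on each other. The labels and the 0.15 rule recur for the two-factor secondary analyses in 5.3.2, and 5.6 makes the moderator analyses conditional on a significant primary interaction.

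**Working it through.** **Inputs.** From SAP 2.3: f = 0.22, α = 0.05, power 80%, 168 evaluable patients (42 per group). From 3.1: two-sided tests. From 2.1: allocation 1:1:1:1. The SAP gives no effect in SD units, so the step sizes below are assumptions. SD means the residual SD.

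**The plan's own figure.** A non-central F test with 4 groups, 1 numerator degree of freedom and λ = f²N first reaches 80% power at N = 165, which rounds to 168 for equal groups. At N = 168, λ = 0.22² × 168 = 8.13 and power is 80.9%. The figure reproduces, so the trial is sized for a one-degree-of-freedom effect such as the interaction. For that contrast f = 0.22 corresponds to 4 × 0.22 = 0.88 SD.

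**The contrast.** I = (OD−OC) − (HD−HC) = (OD−HD) + (HC−OC). This identity needs no assumption. In the ordering of 5.3.2, OD−HD is the moderate-to-high step off drug and HC−OC is the low-to-moderate step on drug.

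**Additive truth.** Let b be the drug effect and g(L), g(M), g(H) the expectation effects:

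- OD = b + g(H), HD = b + g(M), HC = g(M), OC = g(L)
- I = [g(H) − g(M)] + [g(M) − g(L)] = g(H) − g(L); b cancels.

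**Size.** SE(I) = √(4/42) = 0.31 SD.

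| Truth (assumed) | I | Interaction significant |
|---|---|---|
| No expectation effect | 0 | 5% |
| Additive, steps 0.20 and 0.20 SD | 0.40 | about 25% |
| Additive, steps 0.44 and 0.44 SD | 0.88 | about 81% |
| Expectation acts only off drug: OD−HD = 0.88, HC−OC = 0 | 0.88 | about 81% |
| Steps of opposite sign: OD−HD = −0.44, HC−OC = 0.44 | 0 | 5% |

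Rows three and four give the same I and the same rejection rate, although only row four has effect modification (with equal underlying expectation steps). Row five is a drug-by-expectation interaction that the test misses.

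**Fallback when p > 0.15, additive truth.**

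- Treatment main effect: [(OD−OC) + (HD−HC)]/2 = b + [g(H) − g(L)]/2. With b = 0 and steps of 0.44 SD, simulation (20,000 trials, considered without the 0.15 gate) finds it significant in about 80%.
- Open/hidden main effect: [(OD−HD) + (OC−HC)]/2 = [g(H) + g(L)]/2 − g(M), which is 0 for equal steps. It is significant in 5% although the low-to-high effect is 0.88 SD.

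**The difference of the steps.** (OD−HD) − (HC−OC) = OD + OC − HD − HC, twice the open/hidden main effect. With equal steps it is 0 in row three (5% significant) and 0.88 in row four (81%). In an additive truth with unequal steps of 0.68 and 0.20 SD it is 0.48 SD and significant in about 34%, with no effect modification at all.

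**The case against.** The 2×2 factor is defined by the information given, and the first hypothesis names that factor. A significant result is therefore an interaction of two randomised factors and supports the hypothesis as literally worded. The Posner variable is explicitly a different one, for one secondary endpoint. Type I error, randomisation and sample size are untouched, and the protocol, which is not at hand, may explain the open-hidden rationale. All of this stands. What remains is that 1.2 sets directions for the DESS that imply the Posner ordering, so the word expectation in the conclusion would mislead.

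Post-hoc subgroup comparisons with adjusted mean differences and 95% confidence intervals are also planned already. That stands in part: 5.3.1 does not name the comparisons, and it does not assure them once the interaction has been dropped.

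Three stronger readings are tempting, and the SAP supports none of them:

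- *The interaction simply is the low-to-high expectation effect.* That equality needs additivity; without it, I is only the sum of two steps, each within one drug condition.
- *A significant result shows only that expectation matters.* If expectation acts only off drug, the effect modification is real and the test responds to it. It just cannot tell this case from the additive one.
- *The open/hidden main effect is the correct test of effect modification.* That holds only if the two expectation steps are equal on the DESS scale, as the 34% above shows. Continuation with high symptom expectation and discontinuation with low symptom expectation are not among the arms, so no contrast removes this limit.

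**Conclusion.** The point holds as one of labelling and interpretation, and should be fixed. The identity I = (OD−HD) + (HC−OC) is exact. The reading of OD−HD and HC−OC as expectation steps rests on the ordering in 5.3.2 and the hypotheses in 1.2. Under additivity the primary test would be significant in about 25% (steps of 0.20 SD) to 81% (0.44 SD) of trials without any drug-by-expectation interaction. These rates rest on assumed steps, 42 evaluable patients per arm and equal variances.

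A significant primary test is valid evidence of an interaction of the randomised factors and of an expectation effect. It does not distinguish additive effects from a drug-by-expectation interaction. The fallback carries the same problem: under additivity its treatment effect includes half the low-to-high expectation effect, and its so-called expectation effect vanishes when the steps are equal.

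A reader might infer that the primary test is invalid or must be replaced. Nothing in the SAP supports that.

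**What to change.** Keep the primary model and the confirmatory test, and change the following:

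- In 1.2, 2.1 and 5.3, rename the second factor as open versus hidden information, and state the implied ordering of symptom expectation (OD high, HD and HC moderate, OC low).
- In 5.3.1, state that the interaction contrast estimates the sum of the two expectation steps, and that significance alone will not be reported as a drug-by-expectation interaction.
- Whatever the interaction p-value, report OD−HD, HC−OC and HD−HC (the drug effect at moderate expectation) with 95% confidence intervals from the four-group model.
- Optionally add (OD−HD) − (HC−OC) as an exploratory contrast, stated to indicate effect modification only if the expectation steps are equal on the DESS scale. The TEX-Q and GEEE expectation ratings scheduled in Table 1 can check the ordering of expectation. They cannot establish that equality, because equal rated steps need not produce equal DESS effects.

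The cost is SAP wording and a few linear contrasts from a model already specified, with no new data. The downside is a narrower conclusion from the primary test.

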2.3 Sample Size

A medium effect size of $f=0.22$, a significance level of $\alpha=0.05$, and a power of 80% were assumed. This resulted in 168 patients needed in total (i.e. 42 per group) using an ANOVA model (with main effects and interactions). Furthermore, with an expected drop-out rate of at most 15%, in total 196 patients need to be recruited (i.e. 49 per group).

Sample size calculation was conducted using G*Power (version 3.1.9.2).

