2.4 Framework

Test for difference will be applied for all endpoints. The primary endpoint is tested in confirmatory manner. A significance level of 0.05 will be used. All secondary and safety endpoints will be analysed in an exploratory way and thus, no adjustment for multiplicity will be applied.

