3.1 Confidence Intervals and *P* Values

All applicable statistical tests will be two-sided and will be performed using a 5% significance level. All confidence intervals presented will be 95% and two-sided. Analyses of secondary and safety outcomes will be performed exploratory without adjustment for multiple testing.

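### Three directional contrasts stated in advance are left exploratory, although testing them by Holm after a significant interaction would put them under error control at no cost in alpha

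*SAP*

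**What the plan says.** Section 1.2 lists five questions. The first is the interaction of treatment and expectation. The next three are directional group contrasts:

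- HC above OC: "Remitted MDD patients who remain on their antidepressant medication will show a higher discontinuation symptom load with moderate than with high expectation".
- HD above HC: patients with moderate expectation "will show a higher discontinuation symptom load if antidepressant medication is discontinued versus if antidepressant medication is continued".
- OD above HD: among patients who discontinue, a higher load with high than with moderate expectation.

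The fifth concerns modulators.

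Section 2.4 states "The primary endpoint is tested in confirmatory manner" and "A significance level of 0.05 will be used". It calls only secondary and safety endpoints exploratory. Section 3.1 adds "All applicable statistical tests will be two-sided and will be performed using a 5% significance level".

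Section 5.3.1 places primary interest in the interaction and then says "The post-hoc comparisons between the subgroups will be addressed exploratively". If the interaction p-value exceeds 0.15, the interaction is dropped and both main effects are assessed. Their status is not given. The SAP has no testing order or multiplicity rule for the three contrasts.

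**The concern.** The same comparisons have two standings. In section 1.2 they are hypotheses fixed in advance with a direction; in section 5.3.1 they are post-hoc and exploratory. The trial aims to separate pharmacological from expectation effects, and these contrasts carry that separation: expectation alone (HC−OC), drug alone (HD−HC), and expectation during discontinuation (OD−HD). The interaction is the sum of the first and the third, so it cannot support a claim on either one, and HD−HC does not enter it as a contrast of its own. Three of the five stated questions therefore have no error-controlled answer, even after a significant primary result.

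**Working it through.** **Inputs.** From section 2.3: "A medium effect size of $f=0.22" and "and a power of 80% were assumed", alpha 0.05, 168 evaluable (42 per arm), 196 recruited (49 per arm). From section 2.1: 1:1:1:1 allocation. The SAP gives neither the split of the interaction between its two parts nor a size for HD−HC, so these are assumptions. Both 42 and 49 per arm are shown, because the primary analysis is intention-to-treat with imputation.

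**The plan's own figure.** Noncentral F, 1 numerator df, 4 groups, noncentrality N·f². The smallest N with 80% power is 165; rounded up to a multiple of 4 it is 168, with power 80.9% (noncentrality 168 × 0.22² = 8.13). At N=196 the noncentrality is 9.49 and power is 86.5%. With 3 numerator df, N would be 230. The stated 168 therefore fits a single 1-df effect such as the interaction.

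**What the interaction can show.** (OD−OC) − (HD−HC) = (OD−HD) + (HC−OC). In a balanced 2×2 layout this contrast equals 4f SD = 4 × 0.22 = 0.88 SD. Its power depends only on the sum: 81% at 42 and 87% at 49 per arm, whether the parts are 0.44 + 0.44 SD or 0.88 SD in OD−HD and zero in HC−OC. The confirmatory result does not tell these two patterns apart.

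**Error control of the fix.** Take the family as the interaction plus the three contrasts.

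- If there is truly no interaction, no contrast is tested unless the interaction is falsely rejected, so any false claim has probability at most 5%.
- If there is an interaction, Holm keeps the chance of any false claim among the three at or below 5%.

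An adjustment within the three is needed: gating on the interaction and then testing all three unadjusted reaches 0.09 when two of them are null. The interaction plus three unadjusted tests gives 0.142 under the global null.

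**Power.** A single contrast of 0.44 SD has standard error √(2/n) SD, so 0.44/0.218 = 2.02 at n=42 and 0.44/0.202 = 2.18 at n=49. Two-sided 5% power is 52% and 58%. Simulating the four cell means (pooled variance, two-sided t tests, interaction first, then Holm) gives these proportions of trials in which each contrast is claimed:

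| Assumed HC−OC / HD−HC / OD−HD (SD) | n per arm | HC−OC | HD−HC | OD−HD |
|---|---|---|---|---|
| 0.44 / 0.44 to 0.50 / 0.44 | 42 | 38–39% | 24–33% | 38–39% |
| 0.44 / 0.44 to 0.50 / 0.44 | 49 | 46–47% | 35–47% | 46–47% |
| 0 / 0.50 / 0.88 | 42 to 49 | about 2% (false) | 34–46% | 80–86% |

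**Why not a sequence in the order of section 1.2.** With all three contrasts at 0.44 SD, the cumulative power for interaction, HC−OC, HD−HC and OD−HD is 81%, 50%, 17% and 6% at 42 per arm, and 87%, 57%, 25% and 10% at 49. In the last pattern of the table, at 49 per arm, that order claims OD−HD in about 1% of trials, against 99% for OD−HD tested alone and 86% for Holm, because testing stops at the null HC−OC.

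**The case against.** The strongest reply is that this is a design preference. The SAP names one confirmatory target, sizes the trial for it and labels the rest exploratory, which is coherent. Post-hoc is also common usage for cell comparisons after a factorial model and need not mean unplanned. Section 5.3.1 reports adjusted means and mean differences with 95% confidence intervals and p-values, so the reader will see both parts of the interaction. Power for the contrasts is modest. Only the first hypothesis names the experimental phase, so tying the others to the primary endpoint is an inference.

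Much of this stands. The exploratory label is permissible, and what is missing is the error-controlled claim, not the estimates. The link to the primary endpoint is inferred, though reasonable, since all four hypotheses use the same outcome. Low power is a reason to state expectations plainly. It does not favour the present plan, under which the chance of an error-controlled claim on these contrasts is zero.

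A reader might infer that the plan inflates the type I error. The SAP does not support that: it makes no confirmatory claim on the three contrasts. If the main effects assessed after p>0.15 were read as confirmatory, the family-wise error under the global null would be 0.133, but the SAP nowhere gives them that status. That point calls for a label only.

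**Conclusion.** The point holds as a missed improvement and an inconsistent label. It does not invalidate the primary analysis. As written, a significant interaction gives no error-controlled answer on HC−OC, HD−HC or OD−HD. Gated Holm testing can only add claims to the current plan. In the scenarios examined it would claim a true contrast in roughly a quarter to a half of trials when effects are 0.44 to 0.50 SD, and in 80–86% when OD−HD is 0.88 SD. These figures assume that f=0.22 is the interaction on the residual SD scale of the model, with equal variances and the effect splits shown.

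**What to change.** Replace the sentence on subgroup comparisons in section 5.3.1, and state the same rule in section 2.4:

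> If the interaction is significant at two-sided 5%, the three prespecified contrasts HC−OC, HD−HC and OD−HD are estimated from the model with the interaction and tested with the Holm procedure at overall two-sided 5%. A hypothesis of Section 1.2 is claimed only if its contrast is significant in the stated direction. If the interaction is not significant, these contrasts, and the main effects assessed after interaction p>0.15, are exploratory.

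A fixed sequence is also valid if its order is justified and fixed before unblinding. The listing order of section 1.2 should not be adopted by default. Add one sentence acknowledging that the sample size was set for the interaction and that power for the contrasts is limited.

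The cost is SAP wording only, to be settled before unblinding.

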5.4 Sensitivity Analyses

In case of a violation of the normality assumption of the residuals, the primary analysis will be repeated with log transformed dependent variable, where appropriate.

Results of the post-hoc group comparisons will then be presented as adjusted mean factors with corresponding 95%- Wald confidence intervals (resulting from back-transformation of the adjusted mean differences) and p-values will be given.

The primary endpoint and the secondary endpoint a) will additionally be analyzed using the complete case data only, without adjustment for baseline discontinuation symptoms, and in the per protocol population.

Further sensitivity analyses on imputed data might be performed, see Section 5.2 for details. All endpoints might be analysed in the per protocol population.

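### The robustness check for non-normal residuals log-transforms the AUC, which tests a different interaction from the primary one, with no rule for outcomes that have no logarithm

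*SAP*

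**What the plan says.** SAP section 5.3.1 fits an ANCOVA to the untransformed DESS AUC (t2-t9), with the two randomised factors, their interaction, the two stratification variables and the t1 value. The interaction is the effect of primary interest, and effects are reported as mean differences. Residual normality is judged from a histogram. If it is clearly violated, "a sensitivity analysis using the log-transformation for the dependent variable will be performed to judge the robustness of the results".

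Section 5.4 repeats this with a qualifier: "the primary analysis will be repeated with log transformed dependent variable, where appropriate". It adds that post-hoc group comparisons from the log model will be back-transformed and shown as mean factors, that is, as ratios. It does not say what the interaction then means or how a disagreement with the primary result is to be read.

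Section 5.1.1 gives the DESS total a range of 0 to 129 and builds the AUC by the trapezoidal rule. No constant is added and no rule for zeros is given.

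Section 5.3.2 applies the same log rule to the other continuous ANCOVA endpoints. These include the change scores in PSS-10 (range -40 to 40) and STADI state anxiety (range -30 to 30) defined in section 5.1.2.

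**The concern.** A robustness check should ask the planned question again with weaker assumptions. For a comparison of two arms, a log repeat usually keeps the null hypothesis roughly intact. For an interaction it does not, because whether an interaction exists depends on the scale. When both main effects are non-zero, the additive interaction can be zero while the multiplicative one is not, and the reverse.

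The log repeat could therefore cast doubt on a sound primary result, or fail to support a real additive interaction, for reasons unrelated to the shape of the residuals. It would also need an unplanned decision, made after seeing the data, on what to do with outcomes that have no logarithm.

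**Working it through.** **Inputs from the SAP.** Four equal arms; alpha 0.05 two-sided; f = 0.22; power 80%; 168 evaluable (42 per arm) and 196 recruited (49 per arm); DESS 0 to 129; visits at weeks 2, 3, 4, 5, 7, 9, 11 and 13.

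**Assumed, because the SAP does not give them.** Mean AUC per arm, log-normal shape, a common CV of 0.6 to 1.0, and the share of zero AUCs. Covariates are left out. Means are listed in the order OD, HD, OC, HC.

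**1. The plan's own figure.** Noncentral F with 1 and N - 4 df and noncentrality N x f². N = 165 gives 80.2%. Rounded up to equal arms, N = 168 has noncentrality 168 x 0.0484 = 8.13 and power 80.9%. The stated 168 reproduces. The sample size is not in dispute; it only sets the arm sizes used below.

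**2. The two contrasts.**
- Raw scale: (OD - HD) - (OC - HC), arithmetic means.
- Log scale: log[(OD/HD) / (OC/HC)], geometric means.

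With a common CV the geometric-mean ratios equal the arithmetic-mean ratios, so:

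| Assumed means | Raw interaction | Ratio interaction |
|---|---|---|
| 180/140/100/60 | 40 - 40 = 0 | 1.286/1.667 = 0.77 |
| 240/160/90/60 | 80 - 30 = 50 | 1.5/1.5 = 1.00 |
| 200/150/75/100 (crossover) | 50 - (-25) = 75 | 1.333/0.75 = 1.78 |

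**3. Rejection rates**, 4,000 simulated trials, 49 per arm, two-sided 5%:

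| Assumed means | CV | Raw test | Log test |
|---|---|---|---|
| 180/140/100/60 | 0.6 | 4-5% | about 35% |
| 180/140/100/60 | 0.8 | 4-5% | about 25% |
| 240/160/90/60 | 0.6 | 47% | about 5% |
| 200/150/75/100 | 0.6 | 89% | 95% |
| 200/150/75/100 | 0.8 | about 66% | about 81% |

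**4. Closed-form check.**
- First row, log scale: variance ln(1 + 0.36) = 0.3075; SE = √(4 x 0.3075/49) = 0.158; |ln 0.771| = 0.260; 0.260/0.158 = 1.64; power is about 1 - Φ(1.97 - 1.64) = 37%.
- Third row, raw scale: SDs 144, 96, 54, 36; SE = √(34,164/49) = 26.4; 50/26.4 = 1.89; power is about 1 - Φ(1.97 - 1.89) = 47%.

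Both agree with the simulation.

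**5. Unequal variance.** With n per arm, the pooled SE² of the contrast is 4 x (Σs²/4)/n = Σs²/n, the same as the unequal-variance SE². This is why the raw test stays at 4-5% in step 3 although the SDs differ threefold. With 38/40/47/47 patients it rises only to about 6-7%.

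**6. Outcomes without a logarithm.** DESS 0 at all eight visits gives AUC = 0; the smallest non-zero AUC is 0.5. If 1% of 168 patients had AUC 0, the chance of at least one is 1 - 0.99^168 = 82%; at 3% it exceeds 99%. The usual remedy, an added constant, moves the answer. In an illustration with the crossover means, 42 per arm, CV 0.8 and zeros in 0/2/10/5% of patients, the ratio interaction was 1.79 with zeros dropped, 2.49 with +0.5, 2.37 with +1, 1.92 with +10 and 1.54 with +50. For the PSS-10 and STADI change scores, every unchanged or improved patient has no log value.

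**The case against.** The strongest reply is that the troublesome patterns are not the ones the trial expects. Section 1.2 hypothesises more symptoms with moderate than with high expectation among continuers, and the opposite among discontinuers. Under such a crossover in means, and with similarly shaped distributions, the log neither creates nor removes the interaction, and the estimated signs agreed in at least 97% of simulated trials. With a drug effect and no expectation effect (180/180/60/60), both tests reject about 4-5%. This stands, and it limits the point: the disagreement needs expectation to act in the same direction in both treatment arms. A reader might infer that the log repeat is never informative. That goes too far, since under a crossover, agreement does suggest that a few very high AUCs do not drive the result.

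A reader might also infer that unequal variance is the larger threat to the primary test. With the planned 1:1:1:1 allocation it is not (step 5). It matters for pairwise post-hoc comparisons, which are exploratory, and slightly if dropout leaves unequal arms.

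On zeros, it may seem natural that they would cluster among open continuers and that those patients would leave the ITT analysis. The SAP gives neither their frequency nor their arm, and it does not say they are dropped; the confirmatory analysis keeps them.

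Finally, the mean-factor wording shows that the ratio scale was recognised, and section 5.4 leaves discretion. Both are fair. But the wording covers only post-hoc comparisons, and discretion is not a zero rule. The qualifier also attaches to the primary analysis, not to the change scores in section 5.3.2.

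**Conclusion.** The point holds as a modest improvement to a conditional sensitivity analysis. The log repeat changes the interaction being tested, so disagreement with the primary model does not show that the primary result is sensitive to non-normality.

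The size depends on means and CVs that the SAP does not give. With same-direction expectation effects the rejection rates can differ as widely as 4-5% against about 35%, or 47% against about 5%. Under the hypothesised crossover both scales point the same way.

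The missing zero rule is a definite gap for the AUC, though how often it would matter is unknown. For the change scores the log rule cannot work as written, because zero and negative values lie inside their stated ranges.

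Nothing here supports a claim that the primary ANCOVA, its alpha or the sample size is wrong.

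**What to change.** In sections 5.3.1, 5.3.2 and 5.4:

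- **Robustness check.** If residuals are clearly non-normal, repeat the same ANCOVA interaction contrast on the untransformed outcome, with a bootstrap interval (patients resampled within randomised group) and HC3 standard errors. HC3 here is the heteroscedasticity-consistent estimator and has nothing to do with the hidden-continuation arm. It earns its place mainly where dropout leaves unequal arms and in the pairwise post-hoc comparisons.
- **Log AUC model.** Keep it, if wanted, only as a supplementary analysis on the ratio scale. Report its interaction as a ratio of geometric-mean ratios, and fix the handling of AUC = 0 before the data are seen.
- **Change scores.** Delete the log rule for PSS-10 and STADI.

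The cost is a few sentences and one more model run. The confirmatory test does not change.
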